For the 75-80% of bladder cancer patients who present with NMIBC, tumour recurrence and progression following TURBT are significant issues, compelling current guidelines to recommend intense long-term surveillance by cystoscopy and urine cytology¹⁵. With the UK prevalence of bladder cancer estimated at 46,500, at any one time there will be 35-37,000 patients with NMIBC requiring such surveillance, performed as often as every 3 to 6 months at an estimated cost of at least £533 per flexible cystoscopy/cytology "episode" (as costed in 2010¹⁶). Around 30% of NMIBC cases will progress to MIBC and require additional therapy.

Around 20-25% of new bladder cancer patients present with *de novo* MIBC^{17,18}. Survival with MIBC remains poor (27-50% five-year survival) and has not improved in 30 years³. The present pathway is largely geared to NMIBC and actively delays effective MIBC treatment, which is often carried out in a different hospital to initial diagnosis and TURBT, increasing handovers and therefore delays. In Birmingham, for example, many National Health Service (NHS) Trusts run haematuria clinics, a smaller number (but at least six) offer systemic chemotherapy, but only two carry out major pelvic surgery and only one radiotherapy. Early clarity on staging and diagnosis would facilitate more coordinated planning and treatment delivery. Similar considerations exist in all major healthcare systems worldwide.

This fragmented care with complicated staging and follow-up leads to the cumulative cost of treating bladder cancer exceeding all other forms of human cancer.

The standard shared patient pathway thus delays therapy for MIBC patients. There is a growing body of opinion that such pathways should separate earlier in order to more appropriately and expeditiously treat MIBC patients⁴, and this is what we propose to evaluate here.

1.2 **Staging and Treatment**

The pros and cons of staging and treatment techniques for bladder cancer are summarised below, including the aim of TURBT in the settings of NMIBC and MIBC.

Table 1.			
Aim of TURBT	NMIBC	MIBC	
Diagnosis	\checkmark	\checkmark	
Staging	\checkmark	Sometimes – understaging in up to 30%	

Table 4 Aim of TUDDT in NMIDC and MIDC

Table 1.	Aim of TURBT in NMIBC and MIBC	
Aim of TURBT	NMIBC	MIBC
Treatment	\checkmark	No – may be harmful
Palliation of symptoms	Sometimes in cases of heavy bleeding	Sometimes in cases of heavy bleeding.

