1.4 Rationale

The prognosis for MIBC remains poor and has not changed for three decades³⁻⁵. Modern MRI approaches now have the ability to accurately stage bladder tumours^{11,19-23} and experimental urinary biomarkers show great promise in identifying MIBC from a urine test with high sensitivity and specificity²⁴⁻²⁶. The platforms therefore exist to improve patient pathways, potentially leading to improved outcomes.

In order to change the current pathway, we need to show that alternatives to TURBT exist for staging, and that faster treatment will improve outcomes.

- 1. Do we need TURBT for histology?
 - a. Flexible cystoscopy can give accurate tumour histological diagnosis and grading but does not assess muscle-invasion.
- 2. Can we replace TURBT for detailed assessment of the bladder tumour?

- a. TURBT is frequently inaccurate and operator dependent up to 30% of tumours assessed as high grade NMIBC at TURBT are subsequently diagnosed as invasive (MIBC) on repeat TURBT or at cystectomy^{6, 27}.
- Buidelines recommend repeat TURBT for patients staged G3pT1 because of the high incidence of under staging – further delaying definitive treatment in some patients with MIBC^{6,27}
- c. Sensitivity and specificity of mpMRI for separating NMIBC from MIBC are 94% and 100%, respectively^{11, 19-23}
- d. Substituting MRI for TURBT should not compromise staging and may improve it.
- 3. Is TURBT an essential component of treatment?
 - a. There are no randomised data on this topic this is one of the aims of this study.
 - b. Evidence exists that TURBT may increase local tumour dissemination²⁸ and lead to increases in circulating tumour cells⁷.
 - c. In most other oncology settings, imaging and biopsy are sufficient for definitive treatment; in some cases imaging alone is sufficient (e.g. kidney cancer and upper tract urothelial cancer). Few tumour sites use an intermediate piecemeal debulking ahead of definitive therapy²⁹.
- 4. Does delaying the correct definitive treatment affect prognosis?
 - Typical duration from first clinic visit to correct definitive treatment within the NHS for MIBC is around 100 days^{17, 30, 31}
 - b. There is evidence that delay can affect prognosis for MIBC¹²⁻¹⁴
 - c. Hence reducing delay should improve prognosis.

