2.2 Outcome Measures

The primary and secondary outcomes change as we go through the study. These are summarised in Table 2.

	Primary Outcomes	Secondary Outcomes
Feasibility stage	The proportion of possible MIBC patients randomised to pathway 2 who correctly follow pathway protocol	 Overall proportion of patients who correctly follow protocol Recruitment and retention rates at each study site Counts of each definitive treatment
Intermediate stage	The time to definitive treatment (TTDT) for all possible MIBC patients	 TTDT for all patients TTDT for probable NMIBC patients Proportion of all patients who correctly follow pathway protocol Recruitment and retention rates at each study site
Final clinical stage	Clinical progression-free survival (CPFS)	 Cost effectiveness of each pathway Patient Quality of life The proportion of patients who correctly follow pathway protocol

Table 2.Primary and Secondary Outcomes

1 1	TTDT for all a socible MIDO a stights
	TTDT for all possible MIBC patients
	 TTDT for all probable NMIBC patients
	TTDT for all MIBC patients
	TTDT for all NMIBC patients
	Time to correct treatment
	Time to each treatment type
	Time to recurrence, progression or metastatic disease progression
	Number of recurrences; progressions and incidence of metastatic disease
	Number of each type of treatment(s) received
	 Accuracy of MRI/TURBT by comparison with histological confirmed diagnoses
	Overall and disease specific survival
	Number of unnecessary radical cystectomies
	Number of SAEs

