7. STUDY PROCEDURE

The study is comparing TURBT with MRI for the assessment of possible MIBC. Patients will be randomised to either pathway 1 or 2 following their cystoscopy result and confirmation of suspicion of NMIBC or MIBC.

7.1 Standard Pathway 1

The current standard of care pathway comprises flexible cystoscopy in clinic combined with upper tract imaging and potentially cross sectional imaging of the bladder/pelvis. The establishment of such 'rapid access', 'urgent referral' or 'haematuria clinics' was first described in 1994^{35, 36}.

Patients with a bladder lesion then undergo rigid cystoscopy with tumour excision (TURBT under general anaesthesia). The exophytic component of the tumour is excised together with underlying detrusor muscle and both samples undergo definitive histopathological diagnosis. The clinical stage of the bladder tumour is also evaluated under anaesthesia.

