7.1.1 TURBT

Transurethral resection of the bladder tumour should be conducted as recommended by the European Association of Urology (EAU) and British Association of Urological Surgeons (BAUS). In particular, resection of the exophytic component should be performed using a rigid resectoscope. Sampling of the underlying detrusor muscle is necessary, as is recording of the clinical stage following resection (complete, incomplete, semi-fixed, fixed mass etc.). Bladder neck or urethral sampling should be performed in patients suitable for neobladder reconstruction. Sampling of areas suspicious of carcinoma in situ (red areas or fluorescent with blue light) should be undertaken. A separate biopsy of the bladder tumour base should be taken. All samples should be sent for histopathological reporting and reviewed at a suitable clinical meeting.

7.2 Image-directed Pathway 2

Instead of TURBT, patients identified as possible MIBC patients will undergo mpMRI.

Criteria for diagnosing patients as possible MIBC are as follows:

- 1. Appearance on flexible cystoscopy
 - This includes the presence of a solid tumour in the bladder or a tumour seen infiltrating into the bladder wall or a solid tumour or mixed solid/papillary morphology.
 - This may also include the presence of a semi-fixed mass within the bladder found by examination before or after the flexible cystoscopy.
- 2. Cytological: The presence of high grade urothelial cells in either the urine cytology or in the flexible cystoscopy biopsy
- 3. If suitable, imaging obtained (e.g. CT Urography). This may also be used to identify possible MIBC.

The endoscopist carrying out the flexible cystoscopy will be asked to assess the likelihood that a bladder tumour is muscle invasive. If yes, and if either urine cytology or a biopsy taken at cystoscopy confirms the presence of high grade urothelial cancer cells then randomisation between pathways 1 and 2 is permitted.

Treatment proceeds via the standard pathway (without randomisation) for patients with either low grade histology or inconclusive visual appearances on cystoscopy.

7.2.1 mpMRI

Imaging will be carried out as per the Imaging Manual. The scans should be initially read at the local centre but secondary central reading by a certified radiologist will be performed for quality assurance and further research purposes.

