13. STATISTICAL CONSIDERATIONS

13.1 Definitions of outcome measures

The proportion of possible MIBC patients randomised to pathway 2 who correctly follow pathway protocol

Defined as the number of possible MIBC patients randomised to pathway 2 who have an MRI as a proportion of all possible MIBC patients randomised to pathway 2.

Time to definitive treatment

Defined as the interval in whole days between the date of randomisation and the first of: TURBT, systemic chemotherapy, radiotherapy, cystectomy or date of decision for best supportive care only.

Time to correct treatment

For NMIBC patients is defined as the number of whole days between date of randomisation and TURBT.

For MIBC patients is defined as the number of whole days between the date of randomisation and the first date of systemic chemotherapy, radiotherapy, cystectomy or date of decision for best supportive care only.

Clinical progression free survival

Defined as the number of whole days between date of randomisation and one of the following events, whatever occurs first:

- Diagnosis of distant metastases
- Diagnosis of loco-regional nodal recurrence
- Diagnosis of muscle invasive tumour recurrence in the bladder
- Diagnosis of non-muscle invasive tumour recurrence in the bladder
- Diagnosis of upper tract urothelial cancer or urethra
- Death from bladder cancer

Patients with no evidence of clinical progression will be censored at the last date of assessment or date of death if death is not attributed to bladder cancer.

Time to metastatic disease progression

Defined as the number of whole days between the date of randomisation and the date of detection of first distant progression or death from bladder cancer. Patients with no evidence of metastatic disease progression will be censored at the last date of assessment or date of death if death is not attributed to bladder cancer.

Time to loco-regional progression

Defined as the number of whole days between the date of randomisation and the earliest date of detection of loco-regional progression or death from bladder cancer.

Loco-regional progression is defined as recurrence in the bladder +/- local extension and

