13.2.2 Intermediate stage

In this stage, we check that pathway 2 will reduce the TTDT for MIBC patients compared to pathway 1. The estimated sample size for this stage is event driven and requires at least 20 MIBC patients to have definitive treatment across both treatment arms.

To account for patients with longer times on the waiting list being prioritised for treatment, we first assume that the hazard of treatment changes over time and follows a Weibull distribution in both treatment arms. We further assumed that the TTDT in pathway 1 has a median of 100 days and 95th percentile 150 days and the effects of pathway 2 is to reduce the median TTDT to 70 days. Assuming that the distribution of the TTDT pathway 2 follows a Weibull distribution with the same shape parameter as pathway 1 and that the usual proportional hazards assumption holds; the hazard ratio for the two study arms is 3.6. Hence, using the log-rank test, to have 80% power to detect a hazard ratio of 3.6 would require a total of 20 patients with MIBC and to have 90% power would require a total of 20 patients. Around 20-25% of new BC patients present with de novo MIBC. Hence, to recruit a total of 20 MIBC patients, *approximately 80-100 patients will need to be recruited*. At 90%, this would increase to approximately 130 patients.

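### Time to definitive treatment counts TURBT as an event, so for MIBC patients pathway 1 is timed to the staging TURBT and pathway 2 to radical treatment, which is not the endpoint the intermediate stage was powered on

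*Protocol*

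**What the plan says.** Table 2 (section 2.2) gives the intermediate-stage primary outcome as "The time to definitive treatment (TTDT) for all possible MIBC patients". Section 13.1 counts TTDT from randomisation to "the first of: TURBT, systemic chemotherapy, radiotherapy, cystectomy or date of decision for best supportive care only", with no restriction by stage or arm.

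The same section defines a second outcome, Time to correct treatment. For MIBC it ends at "the first date of systemic chemotherapy, radiotherapy, cystectomy or date of decision for best supportive care only", so TURBT does not count. For non-muscle-invasive disease (NMIBC) it ends at TURBT. Table 2 lists this outcome only as a final-stage secondary.

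On the order of care, section 7.1 (pathway 1) says "Patients with a bladder lesion then undergo rigid cystoscopy with tumour excision", and section 7.2 (pathway 2) says "Instead of TURBT, patients identified as possible MIBC patients will undergo mpMRI".

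On the role of TURBT, the treatment row of Table 1 (section 1.2) reads "No – may be harmful" for MIBC, and the text below it describes TURBT in MIBC as mainly a staging procedure.

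On power, section 13.2.2 states "We further assumed that the TTDT in pathway 1 has a median of 100 days and 95th percentile 150 days", with 70 days for pathway 2. Section 1.4 states "Typical duration from first clinic visit to correct definitive treatment within the NHS for MIBC is around 100 days".

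**The concern.** The intermediate stage exists to check that pathway 2 brings MIBC patients to treatment sooner. As defined, the outcome does not time the same thing in the two arms. In pathway 1 TURBT is the next step and stops the clock. In pathway 2 the next step is an MRI, which is not an event, so the clock runs on to chemotherapy, radiotherapy, cystectomy or a decision for best supportive care.

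The step that pathway 2 is meant to remove is thus credited to pathway 1 as definitive treatment. A pathway that starts radical treatment 30 days earlier could be reported as no faster, or as slower. The same definition carries into the final-stage TTDT secondaries for MIBC and possible MIBC patients.

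**Working it through.** **Inputs.** From 13.2.2: pathway 1 median 100 days and 95th percentile 150 days, pathway 2 median 70 days, a common Weibull shape, 20 MIBC patients with definitive treatment, and 20-25% of new patients with MIBC. Allocation is 1:1 (6.1.2). The significance level is not stated; two-sided 5% is assumed and reproduces the plan.

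**Reproducing the plan.**
- Shape: k = ln(ln 20 / ln 2) / ln(150/100) = 1.464 / 0.405 = 3.61.
- Hazard ratio, pathway 2 against 1: (100/70)^3.61 = 3.62, stated as 3.6.
- Events for 80% power (Schoenfeld): 4 × (1.960 + 0.842)² / (ln 3.6)² = 19.1, so 20. Power with 20 events is 82%.
- Recruitment: 20/0.25 = 80 to 20/0.20 = 100.

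The stated figures are therefore right for medians of 100 and 70 days.

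**What stops the clock.**

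| Patient | Pathway 1 | Pathway 2 |
|---|---|---|
| MIBC, TTDT | staging TURBT | radical treatment or supportive-care decision |
| MIBC, Time to correct treatment | radical treatment or supportive-care decision | the same |
| Possible MIBC that proves NMIBC, TTDT | TURBT | TURBT after the MRI |

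The 100 days in 13.2.2 matches the section 1.4 figure for correct definitive treatment, which is the second row. The protocol does not cite 1.4 as the source, but gives no other 100-day figure. In pathway 1, TURBT comes before radical treatment, so if 100 days is the median to radical treatment, the median to TURBT is shorter.

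**Effect on the hazard ratio, confirmed MIBC.** Let t be the pathway 1 median wait for TURBT. The protocol does not give it, so t is an assumption. Keep the shape and the 70-day pathway 2 median: HR = (t/70)^3.61. With 20 events, the chance of a significant result is Φ(±√(20/4) × ln HR − 1.96), with plus for pathway 2 and minus for pathway 1.

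| t (days) | HR | Significant for pathway 1 | Significant for pathway 2 |
|---|---|---|---|
| 30 | 0.05 | >99% | 0% |
| 42 | 0.16 | 98% | 0% |
| 60 | 0.57 | 24% | <0.1% |
| 70 | 1.0 | 2.5% | 2.5% |
| 85 | 2.0 | <0.1% | 35% |
| 100 | 3.6 | 0% | 82% |

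A log-rank simulation with 10 patients per arm agrees: about 94-95% for pathway 1 at 42 days, and about 32% for pathway 2 at 85 days and 74% at 100.

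**Effect among possible MIBC patients.** Section 13.2.1 expects about 50% of patients to be possible MIBC. If every true MIBC is flagged, 20-25% out of 50% gives 40-50% of this group with MIBC. Taking 45% MIBC, 22 patients per arm and the same shape, simulation gives these average hazard ratios:

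| t (days) | No MRI delay before TURBT for NMIBC | Assumed 14-day MRI delay |
|---|---|---|
| 30 | 0.33 | 0.14 |
| 60 | 0.76 | 0.53 |

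At 30 days about 90% or more of simulated trials are significant against pathway 2. The direction is unchanged; the size depends on the NMIBC share and the MRI delay.

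**The case against.** A reader might infer that the outcome must favour the standard pathway by construction, and that the stage will report pathway 2 as slower. The documents do not support that. Reversal needs a median TURBT wait under 70 days, and the protocol gives no such figure. Section 1.1 says that TURBT, histopathology and the multidisciplinary decision together add at least 6-12 weeks, but does not separate out the wait for TURBT. Between 70 and 100 days the comparison is diluted rather than reversed, and even at 60 days only about a quarter of confirmed-MIBC trials would be significant against pathway 2.

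Nor can the hazard ratio of 0.05 be read as the effect on the primary outcome. It is for confirmed MIBC, while the synopsis and Table 2 set the primary outcome in all possible MIBC patients. Many of these will prove to have NMIBC and have TURBT in pathway 2 as well. The protocol also keeps a limited palliative role for TURBT in MIBC.

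The damage has limits. Clinical progression-free survival is unaffected, and Time to correct treatment remains a final-stage secondary, so time to radical treatment can still be estimated.

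Finally, Time to correct treatment depends on MIBC status, which is established after randomisation and by different means: TURBT histology in pathway 1, MRI with biopsy in pathway 2. The protocol itself puts understaging at TURBT at up to 30%.

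All of this stands, and it bears on certainty, size and remedy. None of it removes the contradiction: no section limits TURBT as a TTDT event to NMIBC.

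**Conclusion.** The point holds. The definition of TTDT conflicts with the aim of the intermediate stage, with Table 1 and with the power calculation. This part needs no assumption about waiting times: for MIBC patients the two arms are timed to different events, and the stated hazard ratio of 3.6 and 80% power with 20 MIBC patients belong to a different outcome.

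The size does rest on assumptions: a Weibull shape of 3.61 in both arms, a 70-day pathway 2 median and an assumed TURBT wait. Among confirmed MIBC patients the hazard ratio would be about 0.05 to 0.57 for waits of 30 to 60 days. It would be 1.0 at 70 days and 2.0 at 85, where power is about 32-35%. Among all possible MIBC patients the bias has the same direction, but its size cannot be fixed from the protocol.

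This should be corrected before the intermediate analysis, because it concerns that stage's primary outcome.

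**What to change.** 1. Make Time to correct treatment the intermediate primary outcome. For MIBC, TURBT is not an event; for NMIBC, TURBT is the event. Make the same change to the TTDT secondaries for MIBC and possible MIBC patients.
2. Settle the population. The synopsis and Table 2 set the primary outcome in all possible MIBC patients, while 13.3.2 makes MIBC patients the main analysis and all possible MIBC a secondary one. Either analyse all possible MIBC patients as randomised, or reconcile these sections. In either case restate the 13.2.2 event calculation for the population chosen, since the 100 and 70 days describe MIBC patients only.
3. Assign final MIBC or NMIBC status by one rule and at one common time after randomisation in both arms, from all available staging information. Add a sensitivity analysis for understaging at TURBT.

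The cost is small: wording changes in Table 2, 13.1, 13.2.2 and 13.3.2, and one extra sensitivity analysis. Section 10.1 already lists forms for TURBT, MRI, pathology, decision to treat, chemotherapy, radiotherapy, cystectomy and palliative care. Patient care does not change.

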recurrence outside the bladder but within the true pelvis. Local recurrence will be classified as non-invasive (\leq pT1 including Carcinoma In Situ (CIS)) or invasive (unequivocal clinical or pathological evidence of muscle wall invasion \geq pT2). Regional recurrence includes pelvic lymph node recurrence within the true pelvis. Patients with no evidence of loco-regional progression will be censored at the last date of assessment or date of death if death is not attributed to bladder cancer.

Disease-free survival time

Defined as the number of whole days between the date of randomisation and the earliest date of detection of loco-regional or distant progression, or date of death from bladder cancer.

Patients with no evidence of disease progression will be censored at the last date of assessment or date of death if death is not attributed to bladder cancer.

Overall survival time

Defined as the number of whole days between the date of randomisation and date of death from any cause; patients who do not die during the course of the study will be censored at the date of their last available study assessment.

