13.2.3 Definitive stage

This stage tests the effect of the new image-directed pathway on the longer term clinical endpoints. The anticipated duration is 30 months in 15 regional referral centres. The estimated total sample for this stage is *380 progression events*; or approximately 950 patients with bladder cancer.

For this stage, the primary outcome is clinical progression-free survival and is designed to detect a reduction in progression events in pathway 2 such that the hazard ratio is 0.75. Assuming that the

proportional hazards assumption holds; to detect a hazard ratio of 0.75 with 80% power requires observation of 380 progression events and with 90% power requires observation of a total of 510 progression events. To detect this effect at 2 years follow up, assuming an overall recurrence rate of 40%, will require 950 (80% power) or 1275 (90% power) patients. Similar to the intermediate stage, the power for this stage is event driven and hence will depend on the number of observed events and not the number of patients recruited.

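### The final-stage primary outcome, CPFS, omits non-nodal pelvic recurrence that the protocol's other definitions count, and does not say when persistent or growing bladder tumour becomes an event

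*Protocol*

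**What the plan says.** Section 13.2.3 names the outcome and its purpose: "For this stage, the primary outcome is clinical progression-free survival and is designed to detect a reduction in progression events in pathway 2". Section 13.1 defines CPFS as the time from randomisation to the first of six events:

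- spread to distant sites
- for loco-regional disease outside the bladder, "Diagnosis of loco-regional nodal recurrence"
- for muscle-invasive disease inside it, "Diagnosis of muscle invasive tumour recurrence in the bladder"
- the matching item for non-muscle-invasive disease, also worded as recurrence
- upper tract or urethral cancer
- death from bladder cancer

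Patients without evidence of clinical progression are censored at their last assessment, or at a death not attributed to bladder cancer.

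The same section defines loco-regional progression more widely. It covers bladder recurrence with or without local extension, and also "recurrence outside the bladder but within the true pelvis"; pelvic nodes are given as one part of regional recurrence. Disease-free survival takes over that definition.

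On the pathways, Section 7.2 states: "Instead of TURBT, patients identified as possible MIBC patients will undergo mpMRI". Section 7.1 has pathway 1 patients undergo resection. Section 6.1.2 says that allocation is not blinded.

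**The concern.** There are two gaps in how local failure enters the primary outcome.

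The first is an inconsistency. A recurrence in pelvic soft tissue matches no CPFS item, yet it is an event for loco-regional progression and disease-free survival. Such a patient stays at risk for CPFS, or is censored, until something else on the list happens. After cystectomy no in-bladder event is possible, so for those patients nothing else on the list records this kind of relapse. The synopsis gives reduction of iatrogenic tumour spread as an aim, Section 1.1 raises extravesical dissemination through perforation, and Section 1.4 says "Evidence exists that TURBT may increase local tumour dissemination". Part of that spread is left out of the outcome meant to show the benefit.

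The second is an ambiguity. Recurrence normally presumes that the tumour was first cleared. Section 13.1 itself expects some MIBC patients to receive systemic chemotherapy, radiotherapy or best supportive care. If their bladder tumour persists or grows, the list does not say whether, or on what date, an event has occurred. Because one arm skips the initial resection and assessors know the allocation, the same finding could be labelled differently by arm.

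**Working it through.** **Definitions side by side (all in Section 13.1)**

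| Failure | CPFS (primary) | Loco-regional progression | Disease-free survival |
|---|---|---|---|
| Distant metastasis | event | not an event | event |
| Pelvic nodal recurrence | event | event | event |
| Non-nodal recurrence in the true pelvis | **no item** | event | event |
| Recurrence in the bladder | event | event | event |
| Persistence or growth of a tumour never cleared | not stated | not stated | not stated |
| Upper tract or urethral cancer | event | no separate item | no separate item |
| Death from bladder cancer | event | event | event |

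The third row is the contradiction. The fifth is a gap shared by all three definitions, but it matters most for the primary comparison. CPFS is not narrower in every respect, since it has its own upper tract and urethra item. It is narrower on pelvic relapse.

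**The plan's own figures.** Inputs from Section 13.2.3: HR 0.75, 80% or 90% power, 40% event rate at 2 years. Allocation is 1:1 (Section 6.1.2). The final stage states no alpha; two-sided 0.05 is assumed.

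- Events = 4(z₀.₉₇₅ + z_power)² / (ln HR)².
- 80% power: 4 × (1.960 + 0.842)² / 0.2877² ≈ 380 (stated: 380).
- 90% power: 508 (stated: 510).
- Patients: 380/0.40 = 950 and 510/0.40 = 1275, as stated.

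The sample size reproduces and is not in dispute.

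**Sensitivity, on assumed shares only.** The protocol gives no rate of non-nodal pelvic recurrence or of tumour persistence. Suppose that 2%, 5% or 10% of events go uncounted, for good. Take 380 events in total, and 190 per arm when there is no true effect.

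- *Both arms equally, true HR 0.75.* Events = 380(1 − u); power = Φ(√(events/4) × 0.2877 − 1.96).
- *Pathway 2 only, true HR 1.* Apparent HR = 1 − d; events = 190 + 190(1 − d).
- *Pathway 1 only, true HR 0.75.* Apparent HR = 0.75/(1 − d); events = 380(1 − d/2).

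| Uncounted share | Both arms: events, power | Pathway 2 only: apparent HR, chance of falsely favouring pathway 2 (nominal 2.5%) | Pathway 1 only: apparent HR, power |
|---|---|---|---|
| 2% | 372, 79.3% | 0.98, 3.9% | 0.77, 74% |
| 5% | 361, 78.0% | 0.95, 7.1% | 0.79, 62% |
| 10% | 342, 75.8% | 0.90, 16.9% | 0.83, 41% |

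Equal omission costs little power. Unequal omission matters, and it can act in either direction. The shares are not estimates, and they overstate the effect wherever a failure is later picked up by another item.

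**The case against.** A reader might infer that the gaps favour pathway 2, because resected tumour can recur and count while unresected tumour can grow and not count. The documents do not support that as a net conclusion, for three reasons.

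- For pelvic recurrence the protocol's rationale points the other way. If TURBT spreads tumour outside the bladder, leaving out non-nodal pelvic recurrence hides failures mainly in pathway 1 and works against pathway 2.
- For in-bladder disease, resection in pathway 1 need not be complete. Section 7.1.1 asks for incomplete resection and fixed masses to be recorded, and Table 1 does not regard TURBT as treatment for MIBC. Patients in either arm can therefore start definitive treatment with tumour in place.
- Nodal disease, distant metastasis and bladder cancer death are counted over 5 years of follow-up, so some missed failures become events later.

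It can also be said that the recurrence wording is loose rather than exclusive. Section 13.1 explains loco-regional progression in terms of recurrence, Section 13.3.3 wants both progressions and recurrences captured, and the Recurrence Form in Section 10.1 takes either. A detailed rule for residual disease may also stand in the statistical analysis plan, which is not at hand.

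These points stand. They remove any claim about direction and make the in-bladder issue an ambiguity, not a stated exclusion. They do not touch the pelvic mismatch, which lies between definitions that the protocol itself fixes.

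**Conclusion.** The point holds in two parts of unequal strength. It is firm that CPFS leaves out non-nodal recurrence within the true pelvis while loco-regional progression and disease-free survival include it. This rests only on reading the CPFS list as closed, which is how it is written. It is less firm, but real, that the protocol does not say when a persistent or growing primary tumour becomes a CPFS event, in an open-label comparison where initial resection differs by arm.

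The consequence is a possible arm-dependent bias. Its net direction and size cannot be determined from the documents, and the sensitivity figures show only that modest differential omission would matter against a target HR of 0.75. A finding that the trial is tilted towards pathway 2 would not be justified. Unknown direction is still a good reason to settle the definition before the definitive-stage analysis.

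**What to change.** Two changes to the CPFS list in Section 13.1:

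1. Replace the nodal item with loco-regional recurrence outside the bladder, whether nodal or non-nodal, within the true pelvis, so that it matches the definition of loco-regional progression. State which item takes nodal relapse beyond the true pelvis, so that nothing counted now is lost.
2. Add one event-and-date rule for local progression or persistence of muscle-invasive bladder tumour after definitive treatment, applied in the same way whether or not the tumour was resected at TURBT. The rule should not be tied to unresected tumour, because such an event would fall almost only in pathway 2. The follow-up assessments in Section 7.3 name no imaging or cystoscopy, so the rule must say which finding sets the event date.

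The cost is a protocol amendment to the definition, slightly more and earlier events, and some clinical judgement of progression made with the allocation known. Collection should need little change, because the Recurrence Form already takes local recurrence or progression.
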